### **8.2.10. Patient Global Impression of Change-Itch**

The PGIC-Itch was designed to assess change in itching after being treated with study drug from the specified time point compared with baseline. See the SoA ([Table 1](#)) and [Appendix 9](#) for time points and details.

### **8.2.11. Exploratory Markers of Bile Acid Synthesis, Inflammation, Pruritogens**

Serum 7 $\alpha$ C4 and FGF-19 will be evaluated as markers of bile acid synthesis. Samples will be collected at the times shown in the SoA ([Table 1](#)). Sample collection, processing, and shipping instructions will be provided to the site separately.

Additional biomarkers of inflammation (GLP-1) and pruritogens (autotaxin, progesterone sulfate) will also be evaluated and collected at times shown in the SoA.

## **8.3. Adverse Event Collection**

At each study visit, participants will be questioned in a general way to ascertain whether AEs have occurred since the previous visit (e.g., “Have you had any health problems since your last visit?”). Refer to [Section 9](#) for additional information.

The investigator and/or designees are responsible for detecting, documenting, and reporting events that meet the AE/SAE/AESI/ECI reporting criteria described in [Sections 9.2.1](#) and [9.2.6](#).

### **8.3.1. Time Period for Collection**

All SAEs will be collected from the signing of the ICF until whichever of the following time points comes last: the F2 or up to 30 days after date of discharge from hospital for mother or for the baby, respectively, as specified in the SoA ([Table 1](#)).

All AEs will be collected from first dose of study drug until whichever of the following time points comes last: the F2, or up to 30 days after date of discharge from hospital for mother or for the baby, as specified in the SoA ([Table 1](#)).

All SAEs/AESIs will be reported to the sponsor or designee within 24 hours of the site staff or personnel awareness.

Adverse perinatal events that are included in the key secondary composite endpoint should not be captured as AEs or SAEs because they will already be captured as endpoints for the purposes of efficacy assessment. Refer to [Sections 3.2](#) and [3.3](#) for details.

Medical occurrences that begin before the start of study drug but after obtaining informed consent will be recorded in the medical history/current medical conditions eCRF and not the AE eCRF unless they meet seriousness criteria.

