### 1.3. Schedule of Activities

**Table 1 Schedule of Activities**

Visit Name	Screening	Treatment Period				Follow-Up		Notes
		Baseline	Weeks 1, 2, 3, etc.	Early Termination*	EOT/Delivery	F1	F2 (EOS)	
Day/Week (Window)	Day -10 to -1	0*	Every 7 Days (±1 Day) Until Delivery		Day of Delivery (+2 Days)	Phone Call: 14 Days after Delivery (±3 Days)	Clinic Visit: 28 Days after Delivery (±3 Days)	
*Participants who early terminate from study drug should still continue with weekly visits through delivery, F1, and F2.
 
Some visits may be conducted as a home health or remote visit at the discretion of the investigator upon approval by the sponsor or designee and in accordance with local and regional regulations.
 
*See Section 8.1.8 for further details on timing of baseline visit.

Administrative Procedures								
Informed consent	X							
Eligibility Procedures								
Inclusion/exclusion criteria	X	X						
Demography	X							
Prior/concomitant treatment	X	X	X	X	X	X	X	
Medical history	X	X						Includes menstrual and obstetric history
Estimated gestational age assessment	X							Confirmation of eligibility based upon estimated gestational age required before randomization: CRL from early ultrasound or head circumference on ultrasound if CRL is >84 mm.

Visit Name	Screening	Treatment Period				Follow-Up		Notes
		Baseline	Weeks 1, 2, 3, etc.	Early Termination*	EOT/Delivery	F1	F2 (EOS)	
Day/Week (Window)	Day -10 to -1	0*	Every 7 Days (±1 Day) Until Delivery		Day of Delivery (+2 Days)	Phone Call: 14 Days after Delivery (±3 Days)	Clinic Visit: 28 Days after Delivery (±3 Days)	*Participants who early terminate from study drug should still continue with weekly visits through delivery, F1, and F2.  Some visits may be conducted as a home health or remote visit at the discretion of the investigator upon approval by the sponsor or designee and in accordance with local and regional regulations. *See Section 8.1.8 for further details on timing of baseline visit.
Hepatitis and HIV screen, TSH	X							If HIV results are documented as negative from the current pregnancy in a participant deemed to be low risk by the investigator, HIV at screening visit may be waived.
Dosing Procedures								
Randomization		X						
Study drug dispensing		X	X					As needed
Study drug collection/reconciliation			X	X	X			As needed
Efficacy Procedures								

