AE review		X	X	X	X	X	X	AEs for mother and baby to be collected and reviewed for up to 30 days after respective dates of hospital discharge. See Section 8.3.1 for further details.

Visit Name	Screening	Treatment Period				Follow-Up		Notes
		Baseline	Weeks 1, 2, 3, etc.	Early Termination*	EOT/Delivery	F1	F2 (EOS)	
Day/Week (Window)	Day -10 to -1	0*	Every 7 Days (±1 Day) Until Delivery		Day of Delivery (+2 Days)	Phone Call: 14 Days after Delivery (±3 Days)	Clinic Visit: 28 Days after Delivery (±3 Days)	
*Participants who early terminate from study drug should still continue with weekly visits through delivery, F1, and F2.
 
Some visits may be conducted as a home health or remote visit at the discretion of the investigator upon approval by the sponsor or designee and in accordance with local and regional regulations.
 
*See Section 8.1.8 for further details on timing of baseline visit.

Fetal ultrasound	X*	X*	X**					
* First ultrasound may be done during screening OR baseline (both are not required). The first study ultrasound (screening or baseline) may be waived if an ultrasound was already performed within 1 week prior to screening and should be captured in the eCRF on the screening ultrasound page.
 
** Every 4 weeks while on study drug

Antepartum fetal monitoring (NST/CTG or BPP)		X						At baseline visit only, and thereafter at the discretion of the investigator

Visit Name	Screening	Treatment Period				Follow-Up		Notes
		Baseline	Weeks 1, 2, 3, etc.	Early Termination*	EOT/Delivery	F1	F2 (EOS)	
Day/Week (Window)	Day -10 to -1	0*	Every 7 Days (±1 Day) Until Delivery		Day of Delivery (+2 Days)	Phone Call: 14 Days after Delivery (±3 Days)	Clinic Visit: 28 Days after Delivery (±3 Days)	
*Participants who early terminate from study drug should still continue with weekly visits through delivery, F1, and F2.
 
Some visits may be conducted as a home health or remote visit at the discretion of the investigator upon approval by the sponsor or designee and in accordance with local and regional regulations.
 
*See Section 8.1.8 for further details on timing of baseline visit.

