Perinatal outcomes assessment					X			
Outcomes include
 
 
• Gestational age at delivery
 
• Mode of delivery (e.g., vaginal, operative vaginal, Cesarean, etc.; and iatrogenic vs. spontaneous)
 
• Indication(s) for delivery, if iatrogenic
 
• Maternal estimated blood loss at delivery
 
• Apgar score at 5 minutes
 
• Infant/placenta weight
 
• Presence/absence of meconium staining of amniotic fluid
 
• Neonatal diagnoses and data, including NICU data if applicable
 

Umbilical cord sample (at delivery, when possible)					X			
Umbilical artery pH should be assessed first, followed by volixibat pharmacokinetics. Thereafter, sBA, total cholesterol, LDL cholesterol, and glucose can be assessed in any order.

Genetics – maternal blood (optional)		X						
Specific testing TBD. Must confirm specific consent has been obtained for genetic testing

Visit Name	Screening	Treatment Period				Follow-Up		Notes
		Baseline	Weeks 1, 2, 3, etc.	Early Termination*	EOT/Delivery	F1	F2 (EOS)	
Day/Week (Window)	Day -10 to -1	0*	Every 7 Days (±1 Day) Until Delivery		Day of Delivery (+2 Days)	Phone Call: 14 Days after Delivery (±3 Days)	Clinic Visit: 28 Days after Delivery (±3 Days)	
*Participants who early terminate from study drug should still continue with weekly visits through delivery, F1, and F2.
 
Some visits may be conducted as a home health or remote visit at the discretion of the investigator upon approval by the sponsor or designee and in accordance with local and regional regulations.
 
*See Section 8.1.8 for further details on timing of baseline visit.

Genetics – cord blood sample (optional)					X			Specific testing TBD. Must confirm specific consent has been obtained for genetic testing.
NICU admission					X	X	X	Collect NICU admissions diagnoses and data for the duration of NICU stay (i.e., follow to resolution).
Drug Levels/Biomarkers Procedures								
Volixibat concentration sample (maternal plasma)			X*	X	X			
*At Weeks 1 and 3 visit, 3 hours (±1 hour) post-dose
 
When feasible, maternal sample should be collected as close to time of actual delivery as possible.
 
Drug level sampling may be discontinued in Part 2 pending Part 1 results

Volixibat concentration sample (fetal plasma from umbilical cord at delivery, when possible)					X			Drug level sampling may be discontinued in Part 2 pending Part 1 results

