### 3.2. Secondary Objectives and Endpoints

The following secondary objectives and endpoints are applicable in Part 1 and Part 2.

- To assess the efficacy of volixibat on pruritus due to ICP on the basis of the following endpoint:
  - Mean change from baseline to Week 3 of the treatment period in the weekly average worst daily itch score as measured by the Adult Itch Reported Outcome (ItchRO)
- To assess the impact of volixibat on a composite perinatal outcome in participants with ICP on the basis of the following endpoints:
  - Proportion of participants experiencing one or more of the following:
    - Perinatal death, defined as in utero fetal death after randomization or known neonatal death up to 28 days after birth
    - Spontaneous preterm delivery, defined as delivery at <37 weeks' gestational age following spontaneous onset of preterm labor or preterm premature rupture of the membranes (PPROM)
    - Iatrogenic preterm delivery attributable to ICP or ICP-related complications, defined as delivery at <37 weeks' gestational age resulting from medical intervention (i.e., augmentation/induction of labor or cesarean delivery without prior spontaneous onset of preterm labor or PPROM with one or more of the following as the indication for delivery):
      - Diagnosis of ICP with or without suspected fetal compromise
      - Persistently elevated/increasing sBA
      - Worsening hepatic function
      - Intolerable maternal ICP symptoms
    - Neonatal unit admission for  $\geq 12$  hours from birth until hospital discharge for one or more of the following indications:
      - Respiratory insufficiency/failure with requirement for oxygen supplementation
      - Noninvasive or invasive respiratory support
      - Hemodynamic instability or shock requiring clinical intervention
      - Metabolic acidosis or signs of asphyxia

- Proven infection
- Hypoglycemia or feeding problems requiring intravenous (IV) fluids or tube feeding
- Meconium-stained amniotic fluid and/or its sequelae (e.g., meconium aspiration, etc.)

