## **4.2. End of Study Definition**

The end of the study is defined as the date of the last visit of the last participant in the study. The end of study for individual participants is the completion of the follow-up period after the day of delivery, including completion of follow-up Visit 2 (F2).

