### **9.2.10. Follow-Up**

After the initial AE/SAE/AESI/ECI report, the investigator is required to proactively follow each participant at subsequent visits/contacts. All events will be followed until the event resolves, returns to baseline, stabilizes, is otherwise explained, no further improvement is anticipated based on the medical judgement of the treating physician, or the participant is lost to follow-up.

Investigators are not obligated to actively seek AEs or SAEs after study participants exit the study. However, if the investigator learns of any SAEs that occurred in a participant after study exit and he or she considers the event to be reasonably related to the study drug, the investigator must notify the sponsor within 24 hours after awareness.

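### AE/SAE collection is set to run to 30 days after hospital discharge, but no contact is scheduled after F2 (day 25 to 31), and F2 may fall up to three days before the 28-day neonatal-death window closes

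*Protocol*

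**What the plan says.** Protocol Section 8.3.1 collects SAEs from consent, and AEs from first dose, "until whichever of the following time points comes last: the F2 or up to 30 days after date of discharge from hospital" for mother or baby (quoted from the SAE sentence; the AE sentence sets the same end). The AE review note in Table 1 agrees: "AEs for mother and baby to be collected and reviewed for up to 30 days after respective dates of hospital discharge". Section 8.4.1 refers newborn data to the same period.

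The contact schedule is shorter. After delivery, Table 1 has two contacts. F1 is headed "Phone Call: 14 Days after Delivery (±3 Days". F2 is headed "Clinic Visit: 28 Days after Delivery (±3 Days" and is labelled end of study. Section 4.2 defines the individual's end of study as completion of follow-up, "including completion of follow-up Visit 2 (F2". Section 9.2.10 then says: "Investigators are not obligated to actively seek AEs or SAEs after study participants exit the study".

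Two further rules matter. The composite perinatal endpoint in Section 3.2 counts "known neonatal death up to 28 days after birth". The NICU row of Table 1, marked at delivery, F1 and F2, instructs sites: "Collect NICU admissions diagnoses and data for the duration of NICU stay (i.e., follow to resolution".

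**The concern.** Discharge follows delivery, so a limit of 30 days after discharge falls on day 30 or later, while F2 can be no later than day 31. For almost every mother and infant the stated window outlasts the last planned contact. A site could follow Table 1 and Sections 4.2 and 9.2.10 exactly and still not deliver what Section 8.3.1 asks. Section 8.3 elicits AEs by questioning at study visits, and no visit remains. Following known events to resolution, which Section 9.2.10 requires, does not detect new ones.

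The newborn safety tables are the main output at stake. SAP Section 7.1.5.1 treats every reported newborn AE as treatment-emergent, and SAP Section 7.5.2 tabulates them. Post-discharge events in infants who go home late would be recorded only if someone volunteers them.

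The second point concerns the third endpoint in the testing hierarchy. Neonatal death counts through day 28, but F2 may take place on day 25. The perinatal outcomes row of Table 1 is marked only at delivery, and no row records infant vital status at day 28. Sections 8.3.1 and 9.1.1 say composite events should not be captured as AEs or SAEs, so SAE reporting is not a dependable backstop.

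**Working it through.** **Inputs.** Delivery is day 0. F2 day *f* = 28 ± 3, so 25 to 31 (Table 1). AE/SAE window end = max(*f*, *d* + 30), where *d* is the discharge day (Section 8.3.1). The neonatal-death window ends on day 28 (Section 3.2). The documents give no lengths of stay, so every *d* below is an assumption.

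**AE/SAE window.** Days with no scheduled contact = max(0, *d* + 30 − *f*).

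| Discharge day (assumed) | F2 on day 25 | F2 on day 28 | F2 on day 31 |
|---|---|---|---|
| 0 | 5 | 2 | 0 |
| 1 | 6 | 3 | 0 |
| 2 | 7 | 4 | 1 |
| 7 | 12 | 9 | 6 |
| 14 | 19 | 16 | 13 |
| 21 | 26 | 23 | 20 |
| 28 | 33 | 30 | 27 |
| 42 | 47 | 44 | 41 |

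At nominal timing the gap is *d* + 30 − 28 = *d* + 2 days. Over the permitted F2 days it runs from *d* − 1 to *d* + 5, with a floor of 0. It is zero only when *f* ≥ *d* + 30. Since *f* ≤ 31, that requires *d* ≤ 1. Where discharge is on or after F2, all 30 post-discharge days lack a scheduled contact; any excess over 30 in the table is inpatient time, for which the NICU row applies if the infant is in that unit.

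**Which tables are affected.** Maternal TEAEs stop 7 days after the last dose (Protocol Section 10.4.2.1, SAP Section 7.1.5.1). Treatment ends on the day of delivery, so that limit falls no later than day 7, before the earliest F2 on day 25. Apart from the special rule for maternal death, the maternal TEAE tables are largely untouched. Newborn AEs have no such cut-off, so the gap falls on them.

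**Neonatal-death window.** Days after F2 = max(0, 28 − *f*). For F2 on days 25, 26 and 27 this is 3, 2 and 1; for days 28 to 31 it is 0. So 3 of the 7 permitted F2 days leave a gap, and the nominal day leaves none.

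**Whose endpoint could change.** An infant still in the neonatal unit is followed for the whole stay, so an in-unit death by day 28 should be recorded. An infant already counted through preterm delivery or a qualifying admission is composite-positive, so a missed death cannot alter the binary result. What remains is a death at home, on days 26 to 28 at most, after an early F2, in an otherwise event-free infant.

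**The case against.** Collection past F2 is required, not forbidden. Section 8.3.1 and the Table 1 note both state it, Section 8.3 makes investigators responsible for detecting events, and known events must be followed until they settle. The limit is worded as a maximum of 30 days. Section 4.2 can also be read as including F2 in a follow-up period without ending that period there, so an infant whose NICU data are still being collected has arguably not exited. All of this stands against a reader who infers that the safety window cannot be delivered or is wholly unobserved. It does not supply a contact: Table 1 labels F2 as end of study, and the reading of Section 4.2 that keeps follow-up open is not stated.

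A reader might also infer bias between arms, because infants discharged later have a longer uncovered stretch. The documents do not support that. F1 and F2 are timed from delivery in both arms of a double-blind comparison, so scheduled coverage from birth is the same for every infant. Later discharge moves the nominal end of the window without shortening the coverage. A difference by arm would need treatment to change length of stay and late events to go unreported, and the documents give no figure for either.

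Finally, a reader might suppose that long-stay infants are the most exposed to a missed death. The reverse holds, because the NICU instruction follows them through the stay. It is also true that 30 days after any discharge is day 30 or later, so a death on days 26 to 28 lies inside the newborn collection period. But no check is scheduled then, and the composite-event exclusion weakens the SAE route.

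**Conclusion.** The point holds as an internal inconsistency with a small endpoint gap attached. For nearly any discharge after day 1, the AE/SAE window in Section 8.3.1 runs past the last scheduled contact, by discharge day + 2 days at nominal F2 timing, and ascertainment in that stretch is passive. Its weight falls on the newborn AE tables. The arithmetic is certain given the schedule; the typical size depends on lengths of stay that the documents do not give.

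The neonatal-death gap is at most 3 days, is zero when F2 is on or after day 28, and can change the composite only for infants at home with no other component event. Its expected frequency cannot be derived from the documents. The primary endpoint, sample size, power and alpha are unaffected. The inconsistency should be corrected, but it does not threaten the trial's main conclusion.

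**What to change.** 1. **F2 timing.** Make the window one-sided so that F2 cannot precede day 28, for example day 28 + 6 days. The width stays at 6 days (31 − 25 = 34 − 28) and no visit is added. Add to Table 1 a record, at F2, of infant vital status through day 28. The death-window gap is then zero for every permitted F2 day. The cost is that some maternal F2 assessments may take place up to 3 days later than now allowed (34 − 31).

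2. **Reconcile Sections 4.2, 8.3.1, 8.4.1, 9.2.10 and Table 1**, in one of two ways:
   - Add one telephone contact of the F1 type at the later of F2 and 30 days after the later discharge of mother or baby, covering AEs/SAEs, NICU outcome and infant vital status, and define the individual's end of study as that contact. The gap becomes zero. The cost is one short call per participant and later close-out where an infant has a long admission.
   - End the stated AE/SAE window at F2 in Section 8.3.1 and the Table 1 note, with Section 8.4.1 following, and state that NICU follow-up to resolution continues beyond it. The cost is wording only, at the price of a shorter newborn safety window.

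The schedule reproduced in SAP Appendix 1 gives the same F2 timing and should be updated to match.

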### 3.1. Primary Objective and Endpoint

Part 1:

- To assess the safety and tolerability of volixibat in participants with ICP on the basis of the following endpoints:
  - Proportion of participants experiencing one or more of the following:
    - Treatment-emergent adverse events (TEAEs), serious adverse events (SAEs), adverse events of special interest (AESIs), events of clinical interest (ECIs), and AEs that lead to discontinuation of study drug
    - Clinically significant laboratory abnormalities

Part 2:

- To assess the efficacy of volixibat on the reduction of elevated sBA concentrations in participants with ICP on the basis of the following endpoint:
  - Mean change from baseline to Week 3 of the treatment period in total sBA concentration

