## 9. SAFETY REPORTING

### 9.1. Safety Parameters and Definitions

#### 9.1.1. Adverse Events

An AE is any untoward medical occurrence in a patient or clinical study participant or the newborn, temporally associated with the use of study drug, whether or not considered related to the study drug. NOTE: An AE can therefore be any unfavorable and unintended sign (including an abnormal laboratory finding or vital sign), symptom, or disease (new or exacerbated) temporally associated with the use of study drug. For the AE collection period, see the SoA (Table 1) and Section 8.3.1.

This includes the following:

- Any abnormal laboratory test results (hematology, clinical chemistry, or urinalysis) or other safety assessments (e.g., radiological scans, vital signs measurements), including those that worsen from baseline, considered clinically significant in the medical and scientific judgment of the investigator (i.e., not related to progression of underlying disease).
- Exacerbation of a chronic or intermittent preexisting condition including either an increase in frequency and/or intensity of the condition
- New conditions detected or diagnosed after study drug administration even though it may have been present before the start of the study

The following events are NOT considered an AE:

- Any clinically significant abnormal laboratory findings, vital signs or other abnormal safety assessments that are associated with the underlying disease, unless judged by the investigator to be more severe than expected for the participant's condition

- An investigational abnormality (e.g., laboratory parameter, vital sign, or ECG) unless the abnormality is considered clinically significant by the investigator based on at least 1 of the following criteria:
  - Induces clinical signs or symptoms
  - Requires active intervention (including referring a participant to a specialist)
  - Requires interruption or discontinuation of study drug
- The disease/disorder being studied or expected progression, signs, or symptoms of the disease/disorder being studied, unless more severe than expected for the participant's condition. Adverse perinatal events that are included in the key secondary composite endpoint should not be captured as AEs or SAEs because they will already be captured as endpoints for the purposes of efficacy assessment.
- Medical or surgical procedure (e.g., endoscopy, appendectomy): the condition that leads to the procedure is the AE

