### 9.1.2. Serious Adverse Events

If an event is not an AE per definition above, then it cannot be an SAE, even if serious conditions are met (e.g., hospitalization for signs/symptoms of the disease under study, death due to progression of disease). An SAE is defined as any untoward medical occurrence that, at any dose:

- Results in death
- Is life-threatening (the term “life-threatening” in the definition of “serious” refers to an event in which the participant was at risk of death at the time of the event. It does not refer to an event, which hypothetically might have caused death if it were more severe.)
- Requires inpatient hospitalization or prolongation of existing hospitalization

Hospitalization signifies that the participant has been detained (usually involving at least a 24-hour stay) at the hospital or emergency ward for observation and/or treatment that would not have been appropriate in the physician's office or outpatient setting. Complications that occur during hospitalization are AEs. If a complication prolongs hospitalization or fulfills any other serious criteria, the event is serious. When in doubt as to whether “hospitalization” occurred or was necessary, the AE should be considered serious.

Hospitalization for elective treatment of a preexisting condition that did not worsen from baseline is not considered an AE.

Hospitalization for delivery is not considered an SAE unless there was prolongation of the hospitalization beyond the normally expected duration for vaginal or cesarean birth; in such situations, the diagnosis responsible for the prolongation of hospitalization should be considered the SAE.

- Results in persistent disability/incapacity

A substantial disruption of a person's ability to conduct normal life functions

This definition is not intended to include experiences of relatively minor medical significance, such as uncomplicated headache, nausea, vomiting, diarrhea, influenza, and accidental trauma (e.g., sprained ankle) that may interfere with or prevent everyday life functions but do not constitute a substantial disruption.

- Is a congenital anomaly/birth defect
- Other situations (Important Medical Events)

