### **7.5.2. Newborn Safety Assessments**

The number and percentage of participants who experienced AEs described below will be provided and summarized by SOC and PT unless otherwise indicated:

- TEAEs
- TEAEs of Grade 3 or higher (by SOC, PT and maximum severity)
- Serious TEAEs

Furthermore, all AEs reported within newborns will be listed separately.

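### Perinatal events that meet the key secondary composite are kept out of AE/SAE capture, so the SAE part of the Part 1 primary safety endpoint and the maternal and newborn AE tables omit them, although they are reported separately as secondary and exploratory endpoints

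*Protocol*

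**What the plan says.** Protocol 8.3.1 (Time Period for Collection) states that adverse perinatal events belonging to the key secondary composite "should not be captured as AEs or SAEs because they will already be captured as endpoints for the purposes of efficacy assessment". Section 9.1.1, in its list of things that are not AEs, says the same: "Adverse perinatal events that are included in the key secondary composite endpoint should not be captured as AEs or SAEs". Section 9.1.2 then adds: "If an event is not an AE per definition above, then it cannot be an SAE, even if serious conditions are met".

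The composite is defined in Protocol 3.2 and repeated in 8.2.3. Its first component is "Perinatal death, defined as in utero fetal death after randomization or known neonatal death up to 28 days after birth". The second begins "Spontaneous preterm delivery, defined as delivery at <37 weeks' gestational age following spontaneous onset of preterm labor" and also takes in births after preterm membrane rupture. The third is "Iatrogenic preterm delivery attributable to ICP or ICP-related complications". The fourth is a neonatal unit stay of at least 12 hours for one of a list of indications.

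The primary objective of Part 1 in Protocol 3.1 is "To assess the safety and tolerability of volixibat in participants with ICP on the basis of the following endpoints". What follows is the proportion of participants with at least one of these: a TEAE, an SAE, an event of special or clinical interest, an AE that ends study drug, or a clinically significant laboratory abnormality. No perinatal outcome is listed. Protocol 10.4.2.1 builds the AE summaries on TEAEs. SAP 7.5.2 builds the newborn safety tables on recorded AEs: "The number and percentage of participants who experienced AEs described below will be provided".

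**The concern.** The composite components are efficacy outcomes, but in a pregnancy trial they are also the fetal and neonatal harms that a reader of the safety section will look for first. The protocol recognizes the overlap. Threatened preterm labor is an AESI (9.2.6), and treatment-related cramping that prompts a visit for threatened preterm labor is a dose-modification criterion (6.2). Under the capture rule the threat counts toward the Part 1 primary safety endpoint, but a spontaneous preterm birth that follows it does not.

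What is at stake is how the safety results read. The SAE and newborn AE tables, taken alone, would show no stillbirths, no neonatal deaths to day 28 and no spontaneous preterm births, whatever happened. Part 1 safety data feed the choice of dose for Part 2 (10.4.4), so the omission should be made good in the safety output itself and not left for the reader to piece together from the efficacy section.

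**Working it through.** The plan gives no figure of its own on this point, so the main check is to follow an event through the rules.

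**1. Does the rule bar the event?** A stillbirth after randomization is the first composite component (3.2). By 8.3.1 and 9.1.1 it is not recorded as an AE or SAE. Death is a seriousness criterion in 9.1.2, but that section first requires the event to be an AE, so the criterion cannot bring it back. The same holds for neonatal death to day 28, spontaneous birth before 37 weeks and ICP-attributable iatrogenic preterm birth. For a qualifying admission the admission itself is barred. Whether the diagnosis behind it is still recorded is unclear, because 9.2.1 asks for the diagnosis to be entered as the AE.

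**2. What stays reportable?** Events outside the definitions: iatrogenic preterm births not attributable to ICP, admissions under 12 hours or for unlisted reasons, and deaths after day 28. Threatened preterm labor remains an AESI.

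**3. Does any safety section add the events back?** Section 8.3.1 points to 3.2 and 3.3. Section 3.2 is the composite. Section 3.3 lists only AE-based and laboratory endpoints and does not mention these events. Protocol 10.4.2.1 and SAP 7.1.6.1 and 7.5.2 tabulate recorded AEs and have no component row.

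**4. Where are the events reported?** As the secondary composite in both parts (3.2), and as exploratory proportions in both parts (3.4; SAP 6.3) for perinatal death, spontaneous preterm birth, ICP-attributable iatrogenic preterm birth and neonatal intensive care admission of at least 12 hours. The last is close to the fourth component but not identical, since it has no list of indications.

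**5. Size in Part 1.** Up to 80 participants randomized 1:1 gives 80/2 = 40 per dose. The endpoint counts each participant once.
- Participant already has another counted event: change = 0.
- Participant has no other counted event: change = 1/40 = 2.5 percentage points.

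So each omitted event moves a dose group's any-event proportion by 0 to 2.5 points.

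**6. How many participants might be affected?** The documents give no expected composite rate. Assuming 10% to 40%:
- Part 1: 0.10 × 80 = 8 to 0.40 × 80 = 32 participants.
- Part 2: 0.10 × 200 = 20 to 0.40 × 200 = 80 participants.

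**7. What could a component table show?** For the rarest component it would be descriptive only. Zero perinatal deaths among 40 gives a one-sided 95% upper limit of 1 − 0.05^(1/40) = 7.2%. Among 80 it is 1 − 0.05^(1/80) = 3.7%.

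**The case against.** The best reply is that nothing is hidden. The composite is a Part 1 endpoint as well as a Part 2 endpoint, and its components are summarized by treatment group. The mITT and safety populations both require at least one dose and differ only in randomized versus received treatment (Protocol 10.2), so a safety-population table would largely repeat planned output. Perinatal assessment sits under Safety Assessments (8.4.1). Section 10.4.2 says that fetal data beyond the Section 3 endpoints are only listed, which can be read as assuming that the Section 3 endpoints are summarized. Part 1 is open label with a data review after about every 20 participants, and nothing confines that review to AE counts. The SAP is written to Protocol Version 1, with a double-blind three-arm Part 1, so its silence says little about the current Part 1.

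Most of this stands, and it rules out two inferences that a reader might draw. One is that a dose could be selected with fetal or neonatal deaths out of sight. That would require the sponsor to disregard its own Part 1 secondary endpoint. The other is that the IDMC would miss an imbalance in Part 2. Its remit covers maternal and fetal safety data and efficacy monitoring (4.1, 11.5.1), and its charter, which sets the report content, is not among the documents.

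The reply does not show that any safety table contains these events. The 10.4.2 sentence can be read as implying it but does not say so. The current protocol alone establishes the omission, without the SAP.

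A further argument is that Part 1 has no placebo, so counting disease outcomes in its tolerability proportion would mix background ICP risk with drug effect. That is a fair reason to leave the primary endpoint's definition alone and use a supplementary row.

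**Conclusion.** The point holds as one about safety tabulation. Composite-qualifying perinatal events are excluded from AE/SAE capture. The SAE part of the Part 1 primary safety endpoint and the maternal and newborn AE/SAE tables omit them, while secondary and exploratory outputs report them.

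The effect on a Part 1 any-event proportion is 0 to 2.5 points per omitted event at 40 per dose. It would be wrong to treat 2.5 points as the usual effect. Gastrointestinal events are described as common with this drug class (6.8.1.1), so many participants may already be counted. If fewer than 40 are enrolled per dose, the ceiling is 1/n. The estimate of 8 to 32 participants in Part 1 and 20 to 80 in Part 2 rests entirely on the assumed 10% to 40% composite rate.

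A reader might also infer that all preterm births and all neonatal admissions are barred. The text does not say that: the bar follows the composite definitions, and the events in step 2 of the working stay reportable.

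**What to change.** Keep recording these events as endpoints, and make four changes.

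- Amend Protocol 10.4.2 and SAP 7.1.6 and 7.5.2 to tabulate the four components and any component, by dose or arm in the safety population, beside the SAE tables. Use the composite's own fourth component, not the intensive care proportion in 3.4.
- For Part 1, add SAE-or-component as a supplementary row and leave the primary endpoint's definition unchanged.
- State that this table goes into each Part 1 data review, the dose-selection interim analysis and every IDMC report.
- Reconcile the reference in 8.3.1 to Section 3.3, which does not mention these events. At the same time, state whether the diagnosis behind a qualifying admission is recorded as a newborn AE.

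The table uses data already planned for collection, so the cost is one extra output. The downside is that the same events appear in both efficacy and safety results, which a footnote can explain.
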